3 STUDY RATIONALE

There is substantial interest in preventing CV and renal disease progression in the Type 2 diabetic. Activation of the renin angiotensin aldosterone axis (RAS) and the mineralocorticoid receptor (MR) results in pro-inflammatory effects. Further the phenomenon of aldosterone escape provides a rationale for MR antagonism in addition to an ACEI/ARB agent. Agents that target the RAAS cascade have shown benefit in Type 2 Diabetics although combined RAS blockade such as using ACEI+ARB or ACEI/ARB+Renin inhibition have met with failure primarily owing to adverse effects such as hypotension and renal failure/hyperkalemia requiring dialysis. It has been speculated that dual RAS blockade or use of ACEI/ARB in conjunction with MRA may potentially be beneficial if one controls hyperkalemia and/or avoid excess hypotension. As a foundation for this current proposal, we have demonstrated an important role for RAAS and MR antagonism in reducing atherosclerosis and inflammation in experimental animal models and limited studies in humans. We are currently testing the efficacy of Spironolactone in reducing atherosclerosis on top of ACEI/ARB in high-risk patients with T2DM with concomitant CKD as part of a Randomized Double-blind controlled clinical

trial. Given the fact that as much as 20-40% of a diabetic patient population with CKD may have problems of hyperkalemia on spironolactone, particularly those already on ACEI/ARB therapy, that would preclude their participation in this trial, we would like to propose an open label supplemental arm to where in patients who are ineligible for participation owing to baseline hyperkalemia or hyperkalemia on the dose escalation phase will be eligible to participate in the PRIMARY-Add on trial. The addition of Patiromer will enable introduction of MRA therapy at therapeutic doses and avoidance of hyperkalemia. We thus propose a prospective open label trial with blinded assessment of end-points (PROBE) study which test the relative safety and efficacy of Patiromer on top of Spironolactone in T2DM on LV mass regression and occurrence of hypokalemia (Co-Primary End-points) as well as its effect on 24-hour ABP at 6 weeks, central aortic blood pressure at 6 weeks, atherosclerosis progression at 12 months and measures of monocyte inflammatory potential. If successful, the studies outlined in this proposal will extend the utility of Patiromer in high-risk diabetics at risk for future CV events and provide new information.

3.1 Risk / Benefit Assessment

All potential patients will be informed of the potential side effect profile prior to enrollment in the study and full informed consent will be utilized.

3.1.1 Risks of an MRI Scan

There are no risks associated with the MRI scan. In our center approximately 10% of patients are genuinely claustrophobic. Side Effects Related to Study Drug

3.1.2 Reproductive Risks

Spironolactone may cause risks to the unborn fetus and or the baby of a nursing mother. Therefore, pregnant women and women who are nursing their babies should not participate in the study. Woman must be either post-menopausal for one year, surgically sterile, or using effective contraception. A pregnancy test will be required at screening for all woman who may become pregnant. A negative test is required for the individual to enroll in the study. Participants who become pregnant will report to the study PI immediately, and stop taking the pills.

Spironolactone can decrease the effectiveness of birth control pills. Women who use oral birth control methods will be excluded from the study. Women of child bearing potential should use another reliable form of contraception. Acceptable methods of birth control include subcutaneous implants, intrauterine devices (IUD), barrier methods, surgical sterility, transdermal birth control patch, and abstinence.

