3.1.1.1 Common Side Effects

- Hyperkalemia: We anticipate that approximately 1% of patients may develop serious hyperkalemia that may warrant discontinuation. However this may be considerably higher in patients with GFR of 40-50 ml/minute who will constitute a minority of the patients in the trial.
- Increases in BUN and creatinine

- Hypomagnesemia
- Gynecomastia or breast discomfort. Gynecomastia is a well-described adverse effect of spironolactone and is related to dose and duration of treatment; we anticipate that approximately 10% of patients may develop gynecomastia that may warrant discontinuation. Generally, discontinuation of treatment results in resolution of gynecomastia.

3.1.1.2 *Other Side Effects*

- Cardiovascular: Vasculitis
- Central nervous system: Ataxia, confusion, drowsiness, headache, lethargy
- Dermatologic: Erythematous maculopapular rash, Stevens-Johnson syndrome, toxic epidermal necrolysis, urticaria
- Endocrine & metabolic: Amenorrhea
- Gastrointestinal: Abdominal cramps, diarrhea, gastritis, gastrointestinal hemorrhage, gastrointestinal ulcer, nausea, constipation, flatulence, vomiting
- Genitourinary: Impotence, irregular menses, postmenopausal bleeding
- Hematologic & oncologic: Agranulocytosis, malignant neoplasm of breast
- Hepatic: Hepatotoxicity
- Hypersensitivity: Anaphylaxis
- Immunologic: DRESS syndrome
- Renal: Increased BUN, renal failure, renal insufficiency
- Miscellaneous: Fever

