9 STUDY TREATMENTS

9.1 Method of Assigning Subjects to Treatment Groups

Up to 50 eligible patients will participate in the study. All study participants will undergo a two week run-in period with Patiromer. Then study medication will be commenced at 12.5 mg Spironolactone and Patiromer 8.4 g/d and escalate to 25 mg Spironolactone over

4 weeks. If needed, to manage K⁺, Patiromer will increase to 16.8 g/d. Then the treatment phase will commence with tolerated dose of Spironolactone along with Patiromer for 48 weeks.

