9.5 Measures of Treatment Compliance

Subjects will be asked to keep a patient diary noting the day and date they take their study drug and any adverse events. They will be asked to bring their patient diary to each study visit along with all used and unused study drug containers.

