11.1 Schedule of Events

11.1.1 Main Study Phase

TABLE 4	SCREEN		RUN-IN PHASE		DOSE ESCALATE				TREATMENT PHASE							
					M2	M2	M 2		M 3	M 5	M 7	M 9	M 11	M 12	M 13	
MONTH*	M1		M1		W5	W6	W8	W9	W11	W17	W25	W33	W41	W45	W53	
WEEK	W 1	W2	W3	W 4												
VISIT NUMBER	0		1		2	3	4	5	6	TF1	7	TF2	TF3	TF4	8	
Screening Labs (Renal function panel, Lipid panel, HbA1C, Urine sample Alb/Creat)	X															
Safety Labs (Renal function panel) Mag level*					X*	X	X	Optional	X*		X					X*
History & Targeted Assessment			X								X					X
EKG			X													
Vital Signs or 24-hour BP SphygoCor cuff * (includes central aortic BP))	X		X		X*		X		X*		X					X
Phone Call										X		X	X	X		
MRI					X				X							X
Research Labs/Monocyte Studies, (including PIP, PIINP, CITP and chemokines CCL2, CX3, CL1, and CCL5)					X				X							X
Insulin/Glucose (HOMA-IR)					X											X
HbA1C					X						X					X
Plasma Renin/Aldosterone					X											X
Medication Log		X				X			X	X	X	X	X	X	X	X
Pill counts					X				X		X					X
Dietary survey/instructions		X														X
Urine sample (Albumin/Creat)		X			X				X		X					X
Spot Urine Na/K/Creat					X											
Interim Event log					X		X		X	X	X	X	X	X	X	X
Questionnaire & Instructions			X													

A complete medical history and physical exam will be performed at baseline and will include a 12-lead electrocardiogram (EKG), cardiovascular risk factor assessment, intercurrent CV events, 7-day physical activity recall, active/passive smoking questionnaires and dietary recall questionnaire. Sitting systolic blood pressure, pulse rate, body weight, interim event logs, pill counts, medication logs will be recorded at most clinic visits. Central aortic blood pressure and pulse wave velocity will be obtained during

visit 2 (base), 6 (mid-point) and 8 (exit) while 24-hour BP will be measured at Visit 2 and 6.

Dietary Na⁺ consumption: Since Na intake is an important determinant of MR responsiveness we will ensure that all patients receive dietary survey/instructions (Visit 0) on maintaining a personalized diabetic diet that is stable and is medium to low in sodium (<4 g). We will obtain Na, K and Creatinine levels (Visit 1) to assess Na intake. The kawasaki formula will be used to estimate 24 hour urine.

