11.2 Clinical Laboratory Measurements

Urinary Na levels, albumin, and creatinine

Serum levels of carboxyl-terminal peptide of procollagen type I (PIP), carboxyl-terminal telopeptide of collagen type I (CITP), and amino-terminal peptide of procollagen type III (PIIINP) and chemokines

Safety labs (BUN, creatinine, electrolytes), HOMA-IR, Hem A1C and Plasma Renin Aldosterone, magnesium

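### The only pregnancy test specified is at screening, with no on-treatment test or missed-period trigger, so the stop-if-pregnant rule rests on participant report and general adverse-event capture

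*Combined protocol and SAP*

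**What the plan says.** Section 3.1.2 (Reproductive Risks) names spironolactone as a possible risk to the fetus. It admits women of childbearing potential who use a non-oral method of contraception, and barrier methods and abstinence count. On testing it says: "A pregnancy test will be required at screening for all woman who may become pregnant". A negative result is needed to enrol. After that the instruction is: "Participants who become pregnant will report to the study PI immediately, and stop taking the pills". Section 13.1 lists a positive pregnancy test among the possible reasons to stop study treatment, without saying when such a test is done.

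Table 4 has no pregnancy-test row. The laboratory list in section 11.2 reads "Safety labs (BUN, creatinine, electrolytes), HOMA-IR, Hem A1C and Plasma Renin Aldosterone, magnesium", together with urinary measures and collagen and chemokine markers; pregnancy is not among them.

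The plan does have general capture. Under section 12.1 the investigator asks about adverse events at each visit. Section 9.5 adds: "Subjects will be asked to keep a patient diary noting the day and date they take their study drug and any adverse events". Table 4 carries a row labelled "Interim Event log", marked at the phone contacts as well as at visits.

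On duration, section 9.1 says: "Then the treatment phase will commence with tolerated dose of Spironolactone along with Patiromer for 48 weeks". The COVID-19 plan in section 11.3 closes enrolment permanently and places all active participants in the treatment phase. It allows an additional prescription when visits cannot be held. The length of that prescription depends on recent bloodwork, blood pressure and heart rate, policy and medical judgment; pregnancy status is not named.

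**The concern.** A stop rule protects a participant only if something activates it. Here the drug is stopped in pregnancy, but no scheduled on-treatment procedure would produce the positive test listed in section 13.1. The general adverse-event channels could pick up a missed period, but no specific question is asked about it and no step leads from such a report to a test.

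The side-effect list adds a complication. Section 3.1.1.2 includes "Endocrine & metabolic: Amenorrhea" and "Genitourinary: Impotence, irregular menses, postmenopausal bleeding", with no frequencies. A participant or investigator could put a missed period down to the drug. That is an inference; nothing in the plan says that it has happened.

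At stake is continued fetal exposure to spironolactone if an early pregnancy goes unrecognised. Outcome capture is a second gap. Section 12.2 makes a birth defect a serious adverse event, but section 12.2.1 ends collection of such events once the final visit is complete, so a birth after that visit falls outside it.

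**Working it through.** **Step 1: does anything on treatment generate a test?**
- Section 3.1.2: one test, at screening. Pregnancy later is self-reported.
- Section 13.1: a positive test is a possible reason to stop, with no timing or trigger.
- Table 4: no pregnancy test at any visit. The absence of the screening test there is clerical, because section 3.1.2 already requires it.
- Section 11.2: none.
- Sections 9.5 and 12.1 and the event log: general adverse-event capture, with no question on menses and no link to a test.

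No on-treatment test and no missed-period trigger is specified.

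**Step 2: how much treatment remains?** Reading the Table 4 columns in order gives Visit 2 = W5, Visit 6 = W11 (start of the treatment phase), first call = W17, Visit 7 = W25, further calls = W33, W41 and W45, Visit 8 = W53.
- Plan's figure (section 9.1): 48 weeks of treatment phase.
- Table 4 treatment phase: 53 − 11 = 42 weeks. The 48 weeks is not reproduced.
- Table 4 from Visit 2: 53 − 5 = 48 weeks. This matches only by including dose escalation.

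The two sources disagree, so both figures are carried. Total spironolactone by the text of section 9.1 is 4 + 48 = 52 weeks, but that includes escalation, which active participants have completed. An amendment now can affect only the remaining 42 or 48 weeks, plus any additional COVID-19 prescription, for which no maximum is given.

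**Step 3: which contacts could carry a check?** Urine is collected at Visits 6, 7 and 8.
- Spacing of urine visits: 25 − 11 = 14 weeks, then 53 − 25 = 28 weeks.
- Spacing with the four calls added: 17 − 11 = 6, 25 − 17 = 8, 33 − 25 = 8, 41 − 33 = 8, 45 − 41 = 4, 53 − 45 = 8 weeks.

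For someone past Visit 7, no urine visit remains before the scheduled exit, so the call question is the only scheduled check that could still change dosing. After W45, only the question before an additional prescription remains.

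**Step 4: can a benefit be quantified?** It would need the number of women of childbearing potential, a pregnancy rate, and the chance that existing capture misses a pregnancy. The documents give none of these. Section 9.1 caps the whole study at 50 patients without a breakdown by sex. Entry is above 45, or above 40 with a known atherosclerotic event. No saving is computed.

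**The case against.** The strongest reply is that the risk is already largely handled. The plan requires a negative screening test and effective contraception, and tells a pregnant participant to report at once and stop the drug. Listing a positive test in section 13.1 presupposes testing when indicated, and nothing prevents an investigator from ordering one. The age limits make pregnancy unlikely. The consent pages were not available, and the content of the questionnaire and instructions row in Table 4 is not shown; either could contain a missed-period instruction.

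Most of this stands, and it is why the point is minor. It does not remove the gap: a test that an investigator may order is not one that the plan requires, and no section in hand connects a missed period to it.

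A second reply is that the phone question is itself participant report, the very thing being criticised. That is fair. The difference is that it is a specific question at a fixed time with a required test behind it. It does not make detection independent of the participant.

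A third is that the COVID-19 plan prioritises safety laboratory tests and vital signs and does not name urine, so urine may not be collected while visits are deferred. That also stands, and the fix allows for it.

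**Conclusion.** The gap is real and minor. In the text available, the stop-if-pregnant rule has no specified on-treatment test or trigger over a remaining period of up to about 42 weeks (Table 4) or 48 weeks (section 9.1), and longer with an additional prescription. The number of women concerned is unknown and may be zero. No endpoint or analysis is affected.

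A reader might infer more than this. Three stronger readings are not supported:
- **That 42 to 48 weeks is a ceiling.** The COVID-19 plan allows dosing to continue beyond it, with no stated maximum.
- **That the fix saves a definite 20 or 28 weeks of exposure.** Subtracting contact gaps from remaining treatment (28 − 8 = 20, or 42 − 14 = 28) assumes that every existing check fails and that a pregnancy goes unrecognised for 28 or 42 weeks.
- **That calls limit exposure to 8 weeks.** Eight weeks is the longest spacing between contacts. A conception shortly before a call may not yet have produced a missed period, so it could pass to the next contact.

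The conclusion assumes that Table 4 is read correctly by column order and that the unseen consent pages and instructions contain no equivalent safeguard.

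**What to change.** For any woman of childbearing potential still on spironolactone:
1. Run a urine pregnancy test on the sample already collected at each remaining in-person visit, or when urine is next obtained if visits are deferred.
2. Ask about missed menses or possible pregnancy at each scheduled call and before any additional COVID-19 prescription.
3. If the answer is positive or unclear, require a negative pregnancy test before spironolactone continues. A positive test leads to the stop in sections 3.1.2 and 13.1.
4. Follow any exposed pregnancy to its outcome beyond the final visit, and say so in section 12.2.1.

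Add the screening test to Table 4 as a clerical correction. If a safeguard already stands in the consent form, cite it in section 3.1.2.

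The cost is a minor amendment, at most three scheduled dipsticks per affected woman (Visits 6, 7 and 8; fewer for anyone further along), one question on calls already planned, and an occasional for-cause test with a short hold of spironolactone.

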3.1.1.1 Common Side Effects

- Hyperkalemia: We anticipate that approximately 1% of patients may develop serious hyperkalemia that may warrant discontinuation. However this may be considerably higher in patients with GFR of 40-50 ml/minute who will constitute a minority of the patients in the trial.
- Increases in BUN and creatinine

- Hypomagnesemia
- Gynecomastia or breast discomfort. Gynecomastia is a well-described adverse effect of spironolactone and is related to dose and duration of treatment; we anticipate that approximately 10% of patients may develop gynecomastia that may warrant discontinuation. Generally, discontinuation of treatment results in resolution of gynecomastia.

3.1.1.2 *Other Side Effects*

- Cardiovascular: Vasculitis
- Central nervous system: Ataxia, confusion, drowsiness, headache, lethargy
- Dermatologic: Erythematous maculopapular rash, Stevens-Johnson syndrome, toxic epidermal necrolysis, urticaria
- Endocrine & metabolic: Amenorrhea
- Gastrointestinal: Abdominal cramps, diarrhea, gastritis, gastrointestinal hemorrhage, gastrointestinal ulcer, nausea, constipation, flatulence, vomiting
- Genitourinary: Impotence, irregular menses, postmenopausal bleeding
- Hematologic & oncologic: Agranulocytosis, malignant neoplasm of breast
- Hepatic: Hepatotoxicity
- Hypersensitivity: Anaphylaxis
- Immunologic: DRESS syndrome
- Renal: Increased BUN, renal failure, renal insufficiency
- Miscellaneous: Fever

3.1.2 Potential Benefits of the Proposed Research to the Subjects and Others

It is possible that there may be a benefit with Spironolactone in terms of organ protection and patients may see benefits relating to reduction of atherosclerotic plaque including reduction in risk for events such as heart attacks, stroke, renal failure and need for hospitalization. The potential benefits must obviously be contrasted with the risk for renal failure and hyperkalemia. Adding Patiromer to Spironolactone in patients with Type 2 diabetes mellitus and chronic kidney disease may reduce blood pressure and left ventricular mass to a greater extent compared to patients with Spironolactone alone, and favorably affect key secondary hemodynamic and inflammatory variables including atherosclerosis progression.

3.1.3 Importance of the Knowledge to be Gained

There is an urgent need for clinical trials aimed at reducing the disproportionate cardiovascular disease burden and mortality in Type II diabetes. The multiple cardiovascular benefits of mineralocorticoid receptor (MR) blockade (using spironolactone or eplerenone) are well recognized in patients *without* Type II diabetes in

the setting of congestive heart failure or myocardial infarction. However, randomized trials of MR Blockade have not been conducted in patients with atherosclerosis. A potential role for MR blockade for slowing atherosclerosis progression as well as influencing cardiovascular outcomes in diabetic patients is only beginning to attract the attention of cardiologists. Patients with atherosclerosis may benefit from MR blockade if, on one end of the spectrum, such intervention is made relatively early in the course of Type II diabetes to slow progression and of atherosclerosis and inflammation or plausibly at the other extreme when patients are already at very high risk patient population for cardiovascular events and mortality. The use of Spironolactone in conjunction with Patiromer in patients with type II diabetes and atherosclerosis has not been well studied. The addition of Patiromer will enable introduction of MRA therapy at therapeutic doses and avoidance of hyperkalemia.

3.2 Safety Evaluations

Change in clinical laboratory findings (e.g. BUN, Creatinine, electrolytes).

Incidence of adverse events.

4. STUDY OBJECTIVES

4.1 Primary Objective

Specific Aim 1: To conduct a prospective open label proof-of-concept clinical trial in 50 patients with Type II diabetes evaluating the effects of MRA + Patiromer on LV mass and plaque regression over 12 months of treatment by MRI. Primary outcome measures will be change in LV mass of patients receiving Patiromer + Spironolactone at the end of 12 months and end-point of safety during this period. An additional co-primary measure will include percent change in atheroma volume (PAV) in the thoracic aorta on Patiromer + Spironolactone at the end of 12 months. Additional secondary measures will include central aortic blood pressure, 24-hour mean systolic blood pressure and measures of insulin resistance (HOMA-IR) at 12 weeks.

4.2 Secondary Objective

Specific Aim 2: To compare monocyte polarization and inflammatory activation (flow cytometry and gene expression) after 6 weeks of Patiromer therapy. Specific Aim 2b: Results from this aim will help provide insights into mechanisms of disease progression and preservation of pathways by Patiromer.

[figure not shown]
5. STUDY DESIGN

OVERALL STUDY DESIGN AND EXECUTION

This will be a multicenter trial that will provide a logical extension to a recently funded NIH sponsored trial to assess efficacy of Spironolactone in patients with Type 2 DM and CKD (GFR 20-90ml/m²) compared to placebo (NCT02169089). In this extension study to

NCT02169089, patients with GFR 20-70 ml/m² who are hyperkalemic at baseline (with or without RAAS therapy) precluding an MRA and/or develop hyperkalemia on an MRA (**FIGURE 3**) will be enrolled and placed on Spironolactone. The primary efficacy variables being LV mass change and in patients treated with Patiromer and MRA. Our hypothesis is that Patiromer use in conjunction with an MRA will result in more effective blood pressure lowering, LV mass regression and plaque regression due to more effective lowering of aldosterone and inflammation. The primary safety variable is development of serious hyperkalemia on treatment in Patiromer+Spironolactone arm. Several secondary variables will be obtained, including monocyte-macrophage inflammatory indices, central aortic blood pressure and 24-hour blood pressure at 6 weeks and arterial compliance.

Figure 3.

6. CRITERIA FOR EVALUATION

6.1 Aim 1A Protocol

[figure not shown]
Cardiac and aortic MRI images will be obtained at Visit 2 and Visit 8. Patients will be imaged on a 3T 32-channel whole-body MR imaging system (Trio 3.0T, Siemens, Erlangen) with maximum gradient amplitude of 60 mT/m and a slew rate of 400 mT/m/ms. The system's integrated body coil will be used for radiofrequency signal transmission. Signal reception will be accomplished with the use of two flexible 6-element phase array body coil matrix in combination with the spine coil. After acquiring the low resolution, images for localization, each patient will undergo trueFISP cine imaging (8–10 short axis and 3 LV long axis with 20–30 cardiac phases depending on heart rate). Additional details on sequence parameters are provided on the Manual of operations. Following acquisition of cardiac MRI images, fat suppressed 3D turbo-spin echo (TSE) images using, dark blood acquisition protocol, based on SPACE sequence with 1mm³ resolution. MRI parameters are as follows: TR/TE= R-R interval/22ms, field of view FOV=320x272 mm², slices per slab 56, averages =1.7, bandwidth-BW=781Hz/px, echo spacing=2.9ms, turbo factor= 45, echo train/slice=3.

Quantitative evaluation:

LV mass estimation: the images from the participating sites will be loaded onto a dedicated workstation (*Leonardo*TM, Siemens Medical Solutions, Erlangen, Germany). Using specialized software (*Argus*TM, Siemens Medical Solutions, Erlangen, Germany), the short-axis views of the heart will be automatically sorted into slice positions (rows)

and cardiac phases (columns). End-diastole (ED) and end-systole (ES) will be visually identified as those phases with maximum and minimum area in a midventricular short-axis view of the LV cavity, using the position of the mitral and aortic valve as an aid to identify the phase of the cardiac cycle. The images will be cropped and zoomed to enhance detection of the myocardium-blood pool and myocardium-fat interfaces.

Endocardial contours will be traced automatically in each of the short-axis views both in ED and ES. To improve the accuracy of the measurement, subsequent manual correction will be performed. In addition, the epicardial contour will be traced in ED. The papillary muscles will be included within both contours and considered ventricular wall, as this method has proven close agreement with pathologic quantifications of myocardial mass (70-72). The contours will lie on the ventricular “side” of the interface myocardium-blood (72). One of the major sources of variability in the analysis of LV function is the correct determination of the most basal slice of the LV, as this moves during the cardiac cycle with longitudinal shortening of the heart in systole (73). In our experience, the LV base is typically located in one slice position in ED and in the contiguous more apical slice in ES. The determination of the most basal slice of the LV both in ED and ES will be aided by simultaneous display of the slice position overlaying the four-chamber cine image used to prescribe the short-axis slices. An equivalent approach will be used for the most apical segment. The criteria for inclusion of the basal slice will follow standard recommendations (74): a rim of ventricular myocardium has to encircle at least 50% of the blood pool area; if both ventricular and atrial myocardium are clearly seen in the same slice, both ends of the ventricular wall are joined by a straight line and the resulting portion is included in the LV quantification; the LV outflow tract is included up to the level of the aortic valve. The sum of the areas contained inside the endocardial contours in ED and ES in each slice, multiplied by the section thickness (Simpson’s method) yields the left ventricular end-diastolic and end-systolic volumes (LVEDV and LVESV respectively) (74, 75). No geometrical assumptions are made and therefore the method can be used in the presence of segmental abnormalities (76). The software automatically adds the interslice gap to the slice thickness. The same approach will be used to calculate LV myocardial volume, defined as the volume between the endocardial and epicardial contours, subsequently multiplied by the specific density of the myocardium (1.05 g/cm³) to obtain LV mass (70). The LV mass will be obtained systematically from ED images (71). Left ventricular stroke volume (LVSV) is calculated as LVEDV-LVESV, and the LVSV times the heart rate will be used to derive the cardiac output (CO). Left ventricular ejection fraction (LVEF) will be quantified using the formula: (LVSV/LVEDV)*100.

Plaque Volume Calculation: For each patient MRI images acquired from baseline and post studies will be co-registered on a workstation (FUSION, Siemens Healthcare, Inc.). Multiplanar images perpendicular to the aorta will be generated from both data sets at the same location and evaluated using a custom designed plaque analysis tool (Terarecon, CA). A dedicated and trained technician will perform manual measurements of lumen cross section area (LCSA) and media-adventitia cross section area or MCSA. Vessel wall area measurements will be generated by subtracting the luminal area from outer border of the vessel wall for the images. Total Plaque Area (TPA) at each time point (1-baseline, 2-post-treatment) for each patient will be defined as the sum of the difference between media-adventitia cross section area (MCSA) and the lumen cross section area (LCSA) in each slice. The change in total plaque volume (ΔTPV) and the percentage change ($\% \Delta TPV$ or PAV) for each of the two groups (Spiro and Placebo) will be calculated as follows:

Formula 1: Derivation of total plaque area (TPA)

$TPA = \sum_{N_{patient}} (MCSA - LCSA)$. Using Formula 1 we will obtain TPA_{base} (baseline) and TPA_{post} (post-treatment) for each patient, where $N_{patient}$ is the number of slices per patient. To account for different number of acquired slices in different patients, the atherosclerotic plaque volume (TPV) for each patient at each time point will be normalized to the median number of slices in that group ($N_{median-group}$) as shown below in Formula 2.

Formula 2: Derivation of total plaque volume (TPV)

$TPV = Z \times \frac{N_{median-group}}{N_{patient}} \times TPA$. We will then obtain TPV_{base} (baseline) and TPV_{post} (end-of treatment) for each patient; Z=slice thickness. The change in total plaque volume (ΔTPV_{group}) and percentage change in total plaque volume ($\% \Delta TPV_{group}$) in each group (Spiro/placebo) will be calculated as indicated in Formula 3 (A and B).

Formula 3: Derivation of absolute change (ΔTPV_{group}) and percent change in atheroma volume (PAV or $\% \Delta TPV_{group}$)

$$\Delta TPV_{group} = \frac{1}{N_{group}} \sum_{patients} (TPV_{post} - TPV_{base}) \quad (A)$$

$$PAV_{group} = \% \Delta TPV_{group} = 100 \times \frac{1}{N_{group}} \sum_{patients} \frac{TPV_{post} - TPV_{base}}{TPV_{base}} = 100 \times \frac{\Delta TPV_{group}}{TPV_{base - group}} \quad (B)$$

where N_{group} is the number of patients in the group. **PAV or % change in total atheroma volume= Primary end-point**

To account for possible different median number of slices $N_{median-group}$ of the two groups, the normalized total plaque volume change in Spiro and placebo will be additionally calculated as: $Normalized \Delta TPV_{group} = \Delta TPV_{group} \times \frac{N_{median-group}}{N_{median-opposite-group}}$.

Secondary End-points: Patients will undergo 24-hour ABP and Central Aortic Blood pressures using a validated device (Oscar 2™system from SunTech Medical®), measuring BP at 15-minute intervals during the day (07.00 h–22.00 h) and at 30-minute intervals during the night (22.00 h–07.00 h), was used to measure ABPM. Aldosterone and HOMA-IR measurements after overnight fast after resting for 30 minutes after arrival and prior to IV placement and/or MR assessment. Fasting (9 hour) basal insulin sensitivity will be measured by the validated HOMA-IR index. $HOMA-IR = \text{insulin } (\mu\text{U/mL}) \times \text{glucose } (\text{mmol/L}) / 22.5$ (77). 24-hour ABP will be performed at visit 2 and visit 6.

6.2 Aim 2 Monocyte and Inflammation Studies: Peripheral blood mononuclear cells (PBMC) will be isolated via and purified with anti-human CD14 mAb immobilized on magnetic beads using the MACS system (Miltenyi Biotec) and purity confirmed by flow cytometry. Isolated cells will be lysed for RNA purification (see below). A portion of the PBMCs will be frozen at -80°C in RPMI medium with 20% FBS and 10% DMSO (1x10⁷cells/vial) for concurrent future flow analysis. This protocol has been shown to not affect future analysis of surface marker staining (78). We have considerable experience performing flow analysis in batched frozen monocytes to enhance reproducibility. Multicolor flow cytometry analysis will be performed using Anti-human CD14, CD16, CD206, and CD163 antibodies (BD Biosciences). Analysis will initially enumerate the quantity of CD14^{hi}CD16^{lo}, CD14^{hi}CD16^{hi} and CD14^{lo}CD16^{hi} monocytes which are similar to what has been described (79). The CD14^{hi}CD16^{hi} and CD14^{lo}CD16^{hi} monocytes are believed to represent inflammatory monocytes in the human. Isolated mRNA will be analyzed for classic inflammatory genes (M1) M2 markers (alternate activation) as well as candidate miRs.

